14.3 Quality assurance audits and regulatory agency inspections

The research implementing entity may be subject to audits by the sponsor or its designee. In such a case, the auditor designated by the sponsor shall contact the research implementing entity in advance to determine the date of audit. The auditor may ask to visit the facilities where laboratory specimens are collected and any other facilities used during the clinical research. In addition, this research may be inspected by regulatory agencies, including those of foreign governments (e.g., the Food and Drug Administration [FDA], the United Kingdom Medicines and Healthcare products Regulatory Agency [MHRA]). If the research implementing entity is contacted for an inspection by a regulatory

body, the sponsor should be notified promptly. The principal investigator and the chief executive of the research implementing entity shall ensure that the auditor has access to all the research-related source documents.

15.0 ETHICAL CONDUCT OF CLINICAL RESEARCH

This research shall be conducted with the highest respect for the individual participants (i.e., research subjects) according to the research protocol, and the ethical principles that have their origin in the Declaration of Helsinki, Ethical Guidelines for Medical and Health Research Involving Human Subjects. Each principal investigator shall conduct the study according to regulatory requirements and in accordance with "Responsibilities of the Investigator" in Appendix B.

15.1 Approval of the Ethical Review Board, etc.

The Ethical Review Board, etc., shall be constituted in accordance with the regulations.

The sponsor or its designee should obtain the document listing the name and title of each committee member. When a committee member directly participates in this clinical research, the document describing that he/she is not participating in deliberation or voting for the study shall be obtained.

The sponsor or its designee shall provide related documents for review and approval of the research protocol to the Ethical Review Board, etc. In addition to the research protocol, a copy of the informed consent form and information sheet, written materials related to research subject recruitment, advertisement, and other documents required by regulations, when necessary, shall be submitted to the central committee or a research implementing entity committee such as the Ethics Review Committee to obtain approval. The sponsor or its designee shall obtain records of approval by the Ethical Review Board, etc., for the research protocol and the informed consent form and information sheet before the start of the protocol therapy. The records of approval by the Ethical Review Board, etc., shall include the clinical research title, protocol number, preparation / revision date of the research protocol, and version number and approval date of other reviewed documents (example: informed consent and information sheet). The sponsor shall notify the research implementing entity, the principal investigator, and investigator after confirming the validity of the regulatory documents of the research implementing entity. Protocol procedures such as obtainment of consent shall not be started until the research implementing entity, the principal investigator, and investigator receive notification.

The research implementing entity shall observe all requirements that the Ethical Review Board, etc. prescribe. The requirements may include notifications to committees such as the IEC, for example, revision of the protocol, revision of the informed consent form and information sheet, revision of materials related to research subject recruitment, reports on safety in accordance with the regulatory requirements, reports on status of implementation of the research at intervals determined by a research implementing entity committee such as the Ethics Review Committee, and submission of the study completion report. The sponsor or its designee shall obtain written approval from a

research implementing entity committee such as the Ethics Review Committee related to the above mentioned items and all related materials.

15.2 Conflict of interest

This clinical research shall be conducted with the support of the sponsor.

Prior to the conduction of this clinical research, the investigators involved in this clinical research shall ensure appropriate management of any conflicts (COI) in the conduct of the research in accordance with the rules of the research implementing entity¹¹⁻¹⁵⁾.

The research implementing entity shall comply with all requirements specified by a committee such as the Ethics Review Committee This includes the COI self-statement form, the research protocol, and the informed consent form and information sheet.

15.3 Informed consent and information sheet, and the agreement of the research subjects

The informed consent and information sheet form shall contain specific requirements of the Declaration of Helsinki, Ethical Guidelines for Medical and Health Research Involving Human Subjects and all applicable laws and regulations. The informed consent form and information sheet shall specify the use of personal information and medical information of research subjects in this clinical research (both in and outside Japan: supply to a third party), and disclosure. The informed consent form and the information sheet will explain in detail the nature of the research, its objectives, and potential risks and benefits. Also, the informed consent form will detail the requirements for participation and the fact that research subject is free to withdraw at any time without giving a reason and without any negative effect on the further medical care.

The principal investigator is responsible for the preparation, contents, and approval of the informed consent form and information sheet by the committee such as the IEC. The informed consent form and information sheet must be approved by the committee prior to use.

The informed consent form and information sheet shall be written in language that can be easily understood by the potential research subjects. The principal investigator or investigator shall be responsible for providing detailed explanation of the informed consent form and information sheet to the potential subjects. Information should be given in both oral and written form whenever possible and in manner deemed appropriate by the committee such as the IEC.

The principal investigator or investigator shall ensure that the potential research subjects have (1) an opportunity to inquire about the research and (2) sufficient time to decide on their participation. If a potential research subject decides he or she is willing to participate in the research, then the informed consent form must be signed and dated by the potential research subject prior to entering into the

research as a subject. The principal investigator or investigator shall instruct the potential research subject to sign using their legal names, not nicknames, using a blue or black ball point ink pen. Also the principal investigator or investigator shall sign and date the informed consent form prior to potential research subject entering into the research.

Once signed, the original informed consent form shall be retained by the principal investigator or investigator. The principal investigator or investigator shall record the date that the potential research subject signed the informed consent form in the subject's medical record. A copy of the signed informed consent form shall be given to the research subject.

If the informed consent form and information sheet is revised, the principal investigator or investigator shall newly obtain re-consent from the concerned research subject by following the same procedure as for obtaining the initial consent. The date of obtaining new consent shall be recorded in the research subject's medical record, and a copy of the revised consent form shall be provided to the research subject.

15.4 Personal information of the research subjects

The sponsor or the designee shall affirm the principle of the protection of research subjects' private/personal information, etc. Throughout this study, research subject ID numbers shall be used to link the subject's source data to the sponsor's research database and research-related documents. Limited information on research subjects such as gender, age, and date of birth may be used within the scope of all applicable laws and regulations for identification of research subjects and confirmation of accuracy of research subject ID number.

For verification of the conduct of the research in compliance with this protocol and the Ethical Guidelines for Medical and Health Research Involving Human Subjects, the sponsor shall require the principal investigator to provide the research sponsor's designee, representatives of regulatory authorities, designated auditors, and committees such as the Ethical Review Board direct access to research subjects' original medical records (source data or documents), including laboratory test results, ECG results, admission and discharge records during a subject's research participation, and autopsy reports. The principal investigator or investigator shall obtain specific authorization from the research subject as part of the informed consent process for access to research subject's original medical records by research sponsor's designee and representatives of regulatory authorities (see section 15.3).

When providing a copy of source documents to the sponsor, the principal investigator or investigator shall delete information that may lead to identification of an individual (name and address of research subject, other personal information not recorded on the CRF of the research subject).

15.5 Consultation windows for the research subjects or persons related to the research concerned

The principal investigator shall establish a contact service to respond to inquiries concerning this clinical research from research subjects or concerned people. Details of the contacts for inquiries will be described in the informed consent form

15.6 Financial burden or reward to the research subjects

Of the expenses for this clinical research, the sponsor shall offer compensation for medical treatment not covered by health insurance as research expenses. The research subjects shall pay expenses for medical treatment covered by ordinary health insurance.

In addition, the principal investigator shall pay expenses such as transportation expenses for participation in this clinical research to the research subjects at each visit from the research funds. Details of the financial burden on the research subjects and rewards shall be described in the informed consent form.

15.7 Benefits and inconveniences to the research subjects

15.7.1 Benefits to research subjects

By participating in this clinical research, the research subjects may understand one's own condition of type 2 diabetes mellitus in detail.

15.7.2 Inconveniences to research subjects

By participating in this clinical research the burden of the research subject may increase as number of visits will increase compared to daily medical care.

15.8 Attribution of research results and access rights

15.8.1 Attribution of research results

The research results and data obtained from this research shall belong to the sponsor. In addition, secondary use (metaanalysis, etc.) of the data obtained in this clinical research may be possible if used in such a way that the data shall not be linked to personal identification information.

15.8.2 Data access rights

Access rights for all data and information generated from this study will be given to personnel approved by the sponsor.

15.9 Reporting of results, publication, disclosure, and clinical research registration policy

15.9.1 Reporting of results, publication and disclosure

The principal investigator shall report a written summary of results of the research to the chief executive of the research implementing entity and provide the sponsor with all the results and data obtained from the research. Only the sponsor may disclose the research information to other principal investigators, investigators or regulatory authorities during the research period, except when required by laws and regulations. The sponsor shall be responsible for publication of the research protocol and research-related results (including the public web site) except for other cases permitted in the research contract.

During research period and after the end of research, the sponsor or its designee should promptly summarize the results and present it to medical journals and academic conferences, etc. The sponsor may publish any data or information obtained from the research (including data and information provided by the principal investigator) without obtaining consent of the principal investigator.

The principal investigator or the investigator should obtain the prior written approval from the sponsor when publishing the information obtained in this research at an academic conference, etc.

15.9.2 Clinical research registration

To ensure that information on clinical research is made accessible to the public in a timely manner and to comply with applicable laws, regulations, and guidelines, Takeda Pharmaceutical Company Limited shall register all clinical research being conducted in patients around the world at public trial registration sites, including at least the website(s) of ClinicalTrials.gov (and) Japan Pharmaceutical Information Center Clinical Trials Information (JAPIC). On such websites, the research location (city, country), subject recruitment status, and contact information for Takeda Pharmaceutical Company Limited are open to the public.

15.9.3 Clinical trial results disclosure

Takeda Pharmaceutical Company Limited shall post the research results, irrespective of the nature of the results, at the public trial registration site(s) of Clinical Trials.gov (and) JAPIC in accordance with applicable laws and regulations.

15.10 Insurance and compensation for injury

The research subjects participating in this research shall be compensated for any injury resulting from participation in the research according to local regulations applicable to the research

implementing entity. The sponsor or its designee shall buy an insurance policy to compensate for health injury in research subjects.

Healthy injury in a research subject will be compensated as specified in the study contract. Compensation-related questions by the principal investigator or investigators should be made to the sponsor or its designee.

Appendix A Schedule of Research Procedures

		Observation period Treatment period						
Time of Visit	Week			0			4	Disconti nuation ^{(g}
	Day	-14	-2	1 ^(b)	21 ^(c)	24 ^(c)	29 ^(c)	-
Allowable ran	nge (Day)	-28 to -2	-2	1	21 to 35	24~39 ^(f)	29 to 43	-
VISIT Number	er		1	2	3	4	5	-
Informed procedure	consent	×						
Inclusion/Exc criteria		×	×					
Demographic information		×						
Medical pre-treatment		×	×					
Physical exan		×	×	(\times)	×	×	×	×
Body weight,	BMI		×		×		×	×
Height		×						
Concomitant		×	×	(×)	×	×	×	×
Concurrent di		×	×					
Laboratory te	sts (a)		×		×		×	×
HbA1c			×					
Drug -taking					×	×	×	×
Prescription of therapy and e therapy and a of compliance	xercise ssessment	×	×	(×)	×	×	×	×
1			× (d)	×(d)	× ^(d)	× (d)	×(d)	
CGM			(Sensor insertion)	(Sensor remove)	(Sensor insertion)	(Exchange sensor)	(Sensor remove)	
Self-measurer blood glucose			× (e)	× (e)	× (e)	× ^(e)	× (e)	
Adverse even monitoring	t					X		

- (a) Measured on VISIT1 (Day-2), and the first and ninth days of the 9-day CGM starting on Day 21

 Blood tests: glycoalbumin, 1,5-AG, fasting insulin*, fasting glucagon*, fasting proinsulin*, fasting GLP-1*, fasting GIP*
- (b) The starting day of study treatment in the treatment period is designated as Day 1. The study drug shall be administered after required tests/observations, etc. The day before the start of study treatment in the treatment period is designated as Day -1. It is performed at the visit when principal investigator or investigator consider as needed.
- (c) Trelagliptin 100 mg/week group shall insert the sensor on the day before Trelagliptin administration day. Trelagliptin 100 mg/week shall be administered before breakfast on the day after the sensor insertion day.
 Alogliptin 25 mg/day shall be administered after required tests/observations, etc at every VISIT without taking study drug. Research

subjects shall take study drug prior to the every breakfast at home.

- (d) To be performed by study site personnel
- (e) At leaset, blood glucose levels shall be measured at three time points on the first day of CGM ([1] at least 2 hours after the recorder is

- connected and [2] 2 hours after the first is measured. [3] at bedtime) and at four time points from the second day onward ([1] before breakfast, (2) before lunch, (3) before evening meal, and (4) at bedtime).
- (f) After taking trelagliptin 100 mg/week or alogliptin 25 mg/day on the nest day from sensor insertion on Visit3 (Day 21), research subjects should visit the study site between the third day and the fifth day.
- (g) To be performed to the extent possible

Appendix B Responsibilities of the sponsor

- To appropriately conduct the clinical research in compliance with this research protocol and the Ethical Guidelines for Medical and Health Research Involving Human Subjects and with the highest respect for human rights, safety, and welfare of research subjects.
- To prepare a list of any other investigators and/or research collaborators when certain important
 research-related activities are divided by investigators and/or research collaborators, and submit
 the list to the sponsor as required.
- 3. To prepare the informed consent form and revise it as necessary.
- 4. To check the contents of the study contract.
- 5. To provide sufficient information on the protocol, drug and duties of each personnel to subinvestigators and study collaborators, and give guidance and supervision.
- 6. To select research subjects who satisfy the inclusion criteria, give explanation using written information, and obtain consent in writing.
- 7. To be responsible for all medical judgments related to the research.
- 8. Corresponding to request from the chief executive of the research implementing entity, to report the latest progress status at least once a year to the chief executive of the research implementing entity.
- To ensure that the most update status is confirmed and comprehended regarding the COI of the investigators participating in the clinical research according to the research implementing entity.
- 10. To ensure, together with the chief executive of the research implementing entity, that sufficient medical care is provided to research subjects for all research-related clinically problematic adverse events throughout the period of subjects' research participation and thereafter.
- 11. When a research subject is treated at another medical institution or department, to inform the acting physician at the medical institution or department in writing of the research subject's study participation and research completion/discontinuation after obtaining the research subject's consent, and prepare a record.
- 12. When emergency reporting of serious adverse events, is required, to immediately report it in writing to the chief executive of the research implementing entity and the sponsor.
- 13. To ensure that the CRFs are accurate and complete, electronically sign and submit them to the sponsor.
- 14. To verify any entries on the CRFs made by the investigator or transcribed by the collaborator from source documents, electronically sign and submit them to the sponsor.
- 15. To discuss a revision of the protocol, etc., when proposed by the sponsor.

16. To report the research completion in writing to the chief executive of the research implementing entity.

- Treatment Group: Trelagliptin 100 mg group and Alogliptin 25 mg group

2. TIME WINDOW

For each inspection, observation and evaluation item, evaluable data is handled according to the following table. When there are multiple data that can be evaluated at the same time point, the one with the closest inspection date, observation, and evaluation date to the reference date is adopted, and if the difference from the reference date is the same, the later data is adopted.

[CGM]

Time Point	Reference Date	
Start of the observation	4 hours before breakfast to 20 hours after breakfast at "Day -1"	
period	after the date of administration.	
The 2nd day of the treatment	4 hours before breakfast to 20 hours after breakfast at "Day 1"	
period for CGM insertion	after the date of administration after CGM insertion	
The 3rd day of the treatment	In 24 hours from the end time of "Day 2" after the date of	
period for CGM insertion	administration after CGM insertion	
The 4th day of the treatment	In 24 hours from the end time of "Day 3" after the date of	
period for CGM insertion	administration after CGM insertion	
The 5th day of the treatment	In 24 hours from the end time of "Day 4" after the date of	
period for CGM insertion	administration after CGM insertion	
The 6th day of the treatment	In 24 hours from the end time of "Day 5" after the date of	
period for CGM insertion	administration after CGM insertion	
The 7th day of the treatment	In 24 hours from the end time of "Day 6" after the date of	
period for CGM insertion	administration after CGM insertion	
The 8th day of the treatment	In 24 hours from the end time of "Day 7" after the date of	
period for CGM insertion	administration after CGM insertion	

[Laboratory Tests] Glycoalbumin, 1,5-AG, Fasting Insulin, Fasting Glucagon, Fasting Proinsulin

		Time Allowance
Time Point	Reference Date	Number of days after the
		first administration
Start of the observation	Days after administration: -2	Applicable for Visit 1

		Time Allowance	
Time Point	Reference Date	Number of days after the	
		first administration	
period		(Day -4 to Day -2)	
"Day 1" of week 3-4 of the	Days after administration: 21	Applicable for Visit 3	
treatment period		(Day 19 to Day 35)	
"Day 9" of week 3-4 of the	The number of days after	Applicable for Visit 5	
treatment period	administration is determined as	(Day $1^{*1} + 1$ to Day 43)	
	follows according to the timing of		
	Day 1*1.		
	1. "Day 1 ^{*1} " is days 19 - 25		
	after administration; 29		
	2. "Day 1 ^{*1} " is days 26 - 32		
	after administration; 36		
	3. "Day 1^{*1} " is days 33 - 35		
	after administration; 43		

^{*1} Day1: Days after administration regarded as "Day 1" of treatment period 3-4 week.

[Laboratory Tests] Fasting GLP-1, Fasting GIP, DPP-4 Activity, Inhibitory Rate of DPP-4 Activity

		Time Allowance
Time Point	Reference Date	Number of days after the
		first administration
Start of the observation	Days after administration: -2	Applicable for Visit 1
period		(Day -4 to Day -2)
"Day1" of week 3-4 of the	Days after administration: 21	Applicable for Visit 3
treatment period		(Day 19 to Day 35)
"Day 4" to "Day 6" of week	The number of days after	Applicable for Visit 4
3-4 of the treatment period	administration is determined as	(Day $1^{*1} + 1$ to Day 2^{*2})
	follows according to the timing of	
	Day 1*1.	
	1. "Day 1*1" is days 19 - 23	
	after administration; 24	
	2. "Day 1*1" is days 24 - 30	
	after administration; 31	
	3. "Day 1*1" is days 31 - 35	
	after administration; 38	

		Time Allowance
Time Point	Reference Date	Number of days after the
		first administration
"Day 9" of week 3-4 of the	The number of days after	Applicable for Visit 5
treatment period	administration is determined as	(Day $1^{*1} + 1$ to Day 43)
	follows according to the timing of	
	Day 1*1.	
	1. "Day 1*1" is days 19 - 25	
	after administration; 29	
	2. "Day 1*1" is days 26 - 32	
	after administration; 36	
	3. "Day 1*1" is days 33 - 35	
	after administration; 43	

- *1 Day1: Days after administration regarded as "Day 1" of treatment period 3-4 week.
 ""Day 9" of week 3-4 of the treatment period" will be evaluated prior to ""Day 4" to "Day 6" of week 3-4 of the treatment period"
- *2 Day2: Days after administration regarded as "Day 9" of treatment period 3-4 week.

[Treatment Compliance, Dietetic Therapy, Exercise Therapy]

		Time Allowance
Time Point	Reference Date	Number of days after
		administration
Visit 3	Visit of the time of actual visit	-
Visit 4	Visit of the time of actual visit	-
Visit 5 or time of	Visit of the time of actual visit	-
discontinuation		

- The reference implementation date and the number of days after administration in the treatment period are indicated as "Day -1" for the day before study drug administration and "Day 1" for the administration day.
- The time points of treatment compliance are only Visit5 and time of discontinuation.

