- (f) Research subjects should visit the study site on a day between fourth and sixth day of the 9-day CGM starting on Day 21.
- (g) To be performed to the extent possible

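### The SAP's 'Day 4-6' and 'Day 9' laboratory reference dates cross for sensor insertion on Days 24-25 and 31-32, and the SAP does not say whether visit label or day range then decides the sample

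*SAP*

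**What the plan says.** SAP section 2 (Time Window) opens with a general rule for choosing among samples: "the one with the closest inspection date, observation, and evaluation date to the reference date is adopted". Ties go to the later sample. The stated condition for using the rule is "When there are multiple data that can be evaluated at the same time point", so it has no role where a single result is eligible.

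The table for fasting GLP-1, fasting GIP, DPP-4 activity and its inhibitory rate then sets reference dates in bands of the day adopted as 'Day 1' of week 3-4. That is the Visit 3 sample, taken here as the sensor insertion day.

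- 'Day 4-6' row: the reference is Day 24 for insertion on Days 19-23. The second band, "2. 'Day 1*1' is days 24 - 30", gives Day 31 and the third, "3. 'Day 1*1' is days 31 - 35", gives Day 38.
- 'Day 9' row: the first band, "1. 'Day 1*1' is days 19 - 25", gives Day 29 and the second, "2. 'Day 1*1' is days 26 - 32", gives Day 36. Insertion on Days 33-35 gives Day 43.

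The allowance column gives each row both a visit label and a day range. 'Day 4-6' is labelled for Visit 4, and its range runs from the day after insertion to the date adopted as 'Day 9'. 'Day 9' is labelled for Visit 5, and its range runs from the day after insertion to Day 43. A footnote says that 'Day 9' is evaluated first.

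On timing, Protocol Appendix A footnote (f) says: "Research subjects should visit the study site on a day between fourth and sixth day of the 9-day CGM starting on Day 21". Footnote (a) puts the last sample on the ninth CGM day.

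**The concern.** The two rows describe one visit sequence, so the mid-CGM target should always precede the end-of-CGM target. Because the bands have different cut points (24 and 31 in one row, 26 and 33 in the other), there are insertion days for which it does not. The 'Day 9' target then lies among the days on which Visit 4 is scheduled, and the 'Day 9' day range also contains the Visit 4 date.

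At stake is which sample is reported as end-of-week DPP-4 activity, inhibition, GLP-1 and GIP. A sample from CGM days 4-6 could appear under 'Day 9' while the true ninth-day sample drops out. Two programmers could also read the table differently and produce different datasets. The affected insertion days are not equally open to both arms.

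**Working it through.** **Inputs.** Insertion day d runs from 19 to 35 (Appendix A, Visit 3 range, in the protocol version whose ranges match the SAP table). Visit 4 is on d + k with k = 3, 4 or 5 (fourth to sixth CGM day; Protocol 13.1.3 says third to fifth, but Appendix A and the SAP row label agree on fourth to sixth). Visit 5 is on d + 8. The reference dates are those listed above. This gives 17 × 3 = 51 combinations.

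**Reproducing the SAP's dates.** The references equal d + 3 and d + 8 exactly at d = 21 (24, 29), d = 28 (31, 36) and d = 35 (38, 43). The anchor values are sound; the trouble lies in how far each band stretches.

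**Crossover.**

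| Insertion | 'Day 4-6' reference | 'Day 9' reference | Difference |
|---|---|---|---|
| 23 | 24 | 29 | +5 |
| 24, 25 | 31 | 29 | −2 |
| 26 | 31 | 36 | +5 |
| 30 | 31 | 36 | +5 |
| 31, 32 | 38 | 36 | −2 |
| 33 | 38 | 43 | +5 |

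The references cross on exactly four insertion days. On those days the 'Day 9' target is d + 5 or d + 4 (CGM day 6 or 5), and the 'Day 4-6' target is d + 7 or d + 6 (CGM day 8 or 7).

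**Sample selection if the day range decides eligibility.** Both samples lie between d + 1 and Day 43, so both compete for 'Day 9'. Write R for the 'Day 9' reference. Visit 4 is strictly closer when R − d < (k + 8)/2, which is 5.5, 6 or 6.5 for k = 3, 4 or 5. Ties go to Visit 5, the later sample.

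- d = 24 or 31: R − d = 5, below 5.5, so Visit 4 wins for all three values of k.
- d = 25 or 32: R − d = 4, so Visit 4 wins for all three.
- d = 23 or 30: R − d = 6, so Visit 4 wins only for k = 5 (k = 4 is a tie).
- All other d: R − d is at least 7, so Visit 5 wins.

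Total: 4 × 3 + 2 × 1 = 14 of 51. For example, with insertion on Day 25, Visit 4 on Days 28-30 is 0 or 1 day from Day 29, while Visit 5 on Day 33 is 4 days away. Some of the 51 combinations lie outside Appendix A's visit ranges (Visit 4 on Day 22, for instance), but none of the 14 does.

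Once Visit 4 is adopted as 'Day 9', the 'Day 4-6' range ends on the Visit 4 date. The Visit 5 sample is then excluded from that row too.

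**Sample selection if the visit label decides eligibility.** Only the Visit 5 sample can be 'Day 9', so the closest-date rule has nothing to choose between: 0 of 51.

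**Arms.** Appendix A footnote (c) puts trelagliptin insertion one to three days before a dose. Assuming weekly dosing from Day 1, the relevant doses fall on Days 22, 29 and 36, so insertion falls on Days 19-21, 26-28 or 33-35. None of Days 23-25 or 30-32 is included. Alogliptin insertion has no such constraint.

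**The case against.** The strongest objection is the visit label. The closest-date rule applies only when several results are eligible for one time point. If the label limits 'Day 9' to the Visit 5 sample, a subject on schedule has a single candidate and nothing goes wrong. Two features that seem to favour the day-range reading have other explanations. Evaluating 'Day 9' first is needed in any case, because the 'Day 4-6' range ends at the adopted 'Day 9' date. The early opening of the 'Day 9' range could be meant to admit a discontinuation sample, since Protocol 9.3.5 groups discontinuation with Visit 5. The day-range reading, applied without Appendix A's Visit 4 range, would also let a Visit 4 sample on Day 22 or 23 replace Visit 3 as 'Day 1' for insertion on Day 19, which is hardly intended.

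This stands as far as it goes: mis-selection is not established as fact. It does not settle the matter the other way. The allowance column is headed as a number of days and gives a range in every row. Where the SAP wants assignment by actual visit (the compliance table), it says so and gives no range. With one scheduled sample per visit, a strict visit restriction would leave the banded reference dates with almost nothing to do.

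A reader might also infer that the crossover itself causes the mis-selection. It does not: Days 23 and 30 can fail without any crossover. What matters is how far Visits 4 and 5 lie from the 'Day 9' reference.

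**Conclusion.** Wrong as written, with limited consequences. The reference dates for four insertion days put the earlier time point after the later one on any reading. The choice of sample is ambiguous: 14 of 51 combinations go wrong if the day range governs, and none if the visit label does. These counts assume Visit 4 on CGM days 4-6 and Visit 5 on CGM day 9.

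Three stronger conclusions are tempting but unsupported. First, that the rule always picks the wrong sample on these days: this needs the day-range reading. Second, that 4 to 6 of 17 insertion days (24% to 35%) means that share of alogliptin subjects: these are calendar days, the documents give no distribution of insertion days, and the nominal day is 21. Third, that a treatment comparison is biased: SAP 7.3.1 plans only by-group summaries for these four 'other' endpoints, with no between-group difference. An error confined to alogliptin would distort a side-by-side reading of the arms, but no planned contrast, and that confinement rests on trelagliptin doses staying weekly from Day 1. The primary and secondary CGM endpoints have their own windows and are untouched. The other laboratory table shares the 'Day 9' dates, but those analytes have no Visit 4 sample.

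**What to change.** In the GLP-1, GIP and DPP-4 table, replace the banded dates with offsets from the adopted insertion day: 'Day 4-6' reference = insertion + 4, and 'Day 9' reference = insertion + 8. With these, 0 of 51 combinations go wrong on either reading.

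Also state that only the sample from the labelled visit is eligible for each row, and say how a discontinuation sample is classified. Alternatively, open the 'Day 9' window at insertion + 6, which a scheduled Visit 4 (at most insertion + 5) cannot reach. The eligibility statement matters even with offsets: under the day-range reading, a missed Visit 5 would leave the Visit 4 sample as the only candidate for 'Day 9'.

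Aligning the bands is not sufficient. Using the 'Day 9' bands in both rows leaves the 'Day 9' references unchanged, so all 14 remain. Using the 'Day 4-6' bands in both leaves R − d = 6 at Days 23 and 30, so 2 of 51 remain.

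The cost is a change to the SAP table and the windowing program. No additional data or visits are needed.
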